#### 6.1.1.2. Sensitivity/Supplementary Analyses

For all of the following analyses, standard SAS output will be provided to support the statistical summaries produced but will not be included in the CSR.

The following supplementary analyses to the primary endpoint will be carried out:

- To assume a dose-response relationship with HbA1c (without a baseline interaction) an Emax model will be applied to the LSmeans at Week 16 from the main MMRM analysis as described in Section 5.2.5.
- To assume a dose-response relationship with HbA1c, including an interaction between baseline HbA1c and dose, an Emax model will be applied to the LSMeans at Week 16 from separate MMRM models at the overall baseline HbA1c as described in Section 5.2.6.

CCI

CCI

## 6.2. Secondary Endpoint(s)

### 6.2.1. Response as defined by an HbA1c <7% at Week 16

#### 6.2.1.1. Main Analysis

In all cases the Estimand Set 2 as specified in Section 4 will be utilised.

The proportion of responses at Week 16 will be summarised descriptively by treatment as described in Section 5.2.2, where no imputation for missing values will be conducted. The proportion of responses at Week 16 will also be reported after multiple imputation for missing values as per Section 5.3.

A logistic regression model (as described in Section 5.2.4) will be applied to the response at Week 16 that will be used to estimate the treatment effect related to the secondary Estimand 2 (as described in Section 2.1.2.1), where missing values will be imputed using multiple imputation as per Section 5.3. Baseline HbA1c and strata will be included in the model.

In addition, standard SAS output will be provided to support the main statistical summary table for the logistic regression model and multiple imputation approach but will not be included in the CSR.

#### 6.2.2. Change from Baseline in HbA1c at Weeks 2, 4, 6, 8 and 12

Summaries and analysis results will be reported as per the primary analysis approach (Section 6.1.1).

#### 6.2.3. Change from Baseline in Fasting Plasma Glucose at Weeks 2, 4, 6, 8, 12 and 16

In all cases the Estimand Set 1A as specified in Section 4 will be utilised.

Absolute values and changes from baseline in fasting plasma glucose will be summarised similar to HbA1c in Section 6.1.1.1.

The analysis will be an MMRM (as described in Section 5.2.3) applied to the change from baseline at Weeks 2, 4, 6, 8, 12 and 16 that will be used to estimate the treatment effect related to the primary Estimand 3 (as described in Section 2.1.1). Results similar to HbA1c in Section 6.1.1.1 (excluding the waterfall plot) will be reported along with standard SAS output (where the latter will not be included in the CSR).

#### 6.2.4. Change from Baseline in Body Weight at Weeks 2, 4, 6, 8, 12 and 16

In all cases the Estimand Set 1A as specified in Section 4 will be utilised.

Absolute values and changes from baseline in body weight will be summarised similar to HbA1c in Section 6.1.1.1.

The analysis will be an MMRM (as described in Section 5.2.3) applied to the change from baseline at Weeks 2, 4, 6, 8, 12 and 16 that will be used to estimate the treatment effect related to the primary Estimand 4 (as described in Section 2.1.1). Results similar to HbA1c in Section 6.1.1.1 (including the waterfall plot for changes from baseline at Week 16) will be reported along with standard SAS output (where the latter will not be included in the CSR).

##### 6.2.4.1. Supplementary Analyses

The percentage change from baseline in body weight at Weeks 2, 4, 6, 8, 12 and 16 will similarly be summarised and analysed to absolute changes as per Section 6.2.4.

For the MMRM model, all body weight values (including baseline) will be  $\log_e$ -transformed prior to analysis (i.e. the outcome in the model will be the difference of the  $\log_e$  absolute value at the time point of interest minus the  $\log_e$  baseline). All LSMMeans and LSMean differences (including confidence intervals) will be back-transformed to give geometric LSMMeans and ratios of geometric LSMMeans.

The percent change will then be calculated as follows:

- Percent change =  $100 * (\text{back-transformed LSMean} - 1)$

CCI

[Redacted content]

CCI [Redacted]

[Redacted]

[Redacted]

[Redacted]

[Redacted]

[Redacted]

[Redacted]

[Redacted]

CCI [Redacted]

[Redacted]

[Redacted]

[Redacted]

CCI [REDACTED]

[REDACTED]

[REDACTED]

[REDACTED]

[REDACTED]

## 6.5. Baseline and Other Summaries and Analyses

### 6.5.1. Baseline Summaries

A baseline table (or separate tables, as required) summarizing the following will be produced by treatment and overall: age; gender; race; ethnicity; height; weight; body mass index; duration of T2DM; stratification factor; country; HbA1c; fasting plasma glucose; CCI [REDACTED] eGFR; systolic blood pressure; diastolic blood pressure; and duration of metformin.

This table will also be re-produced limited to each strata. The table restricted to participants on a background of metformin only will not include the strata summary. The table restricted to diet and exercise will not include the metformin dose and strata summary.

### 6.5.2. Study Conduct and Participant Disposition

Participant evaluation groups will show participant disposition for each phase of the study (screening, placebo-run in, double-blind treatment and follow-up) and will additionally show which participants were analysed for efficacy (Estimand Set 1A, CCI [REDACTED] and 2) as well as for safety. Frequency counts and percentages will be supplied for participant discontinuation(s) by treatment and overall.

Data will be reported in accordance with the sponsor reporting standards (including creation of COVID-19 related outputs).

[REDACTED]

CCI

#### **6.5.4. Concomitant Medications and Nondrug Treatments**

All prior and concomitant medication(s) as well as non-drug treatment(s) will be reported according to current sponsor reporting standards.

A separate table listing the use of rescue medication will be produced according to current sponsor reporting standards. The use of rescue medication (grouped by class of medication) will be summarized descriptively by treatment and overall as described in Section 5.2.2. The classes will be defined based on medications used in the study.

#### **6.5.5. Treatment Compliance**

A summary table of treatment compliance (by treatment and overall) will be produced according to current sponsor reporting standards.

#### **6.5.6. Discontinuations**

Participant discontinuations, temporary discontinuations or dose reductions due to adverse events will be detailed and summarised by treatment and overall.

Data will be reported in accordance with the sponsor reporting standards.

Exploratory summaries on the time to discontinuation from the study and time to discontinuation of IP (regardless of study discontinuation or continuation) will be produced separately using Cumulative Incidence Plots as described in Section 5.2.7. For both, participants who discontinue from the study/IP will be censored at the associated discontinuation date.

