### 5.2.7. Cumulative Incidence Plots

Cumulative Incidence Plots will be produced based on the time to the event of interest (starting from the time of start of dosing on Day 1) for each treatment separately and will be plotted on the same graph up to Week 18 (i.e. including the follow-up visit 10). This will be based on plotting the cumulative incidence function (with no competing risks), which will be presented as a % on the y-axis. No statistical testing for differences between treatment will be considered.

Details of censoring are included in Section 6 and example SAS code is provided in Appendix 4.

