## Appendix 4. Traditional Statistical Methodology Details

The following SAS code is to be used as a guide for implementation.

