### Example SAS code for Cumulative Incidence Plots:

```
proc lifetest data = dataset method=km plots=cif(test) outcif=cifatrisk intervals=0 to 20 by 2;
  strata treatment;
  time day*censor(1)/eventcode=0;
run;
```

NOTE: the censor variable has a value = 1 when the related time is censored and has a value = 0 when the event of interest occurs. There should be no other values available for this censored variable in this dataset (including missing values). If required, missing observations should be removed prior to analysis.

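### SAP 6.5.6 censors participants at the very event its time-to-discontinuation plots are meant to show, so followed as written the curves contain no events

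*SAP*

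**What the plan says.** SAP 6.5.6 announces exploratory plots of "time to discontinuation from the study and time to discontinuation of IP (regardless of study discontinuation or continuation"), each to be drawn as described in SAP 5.2.7. The next sentence is the only censoring rule the section gives: "For both, participants who discontinue from the study/IP will be censored at the associated discontinuation date".

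SAP 5.2.7 has no censoring rule of its own: "Details of censoring are included in Section 6". It fixes the estimator ("This will be based on plotting the cumulative incidence function (with no competing risks") and the horizon (the curves "will be plotted on the same graph up to Week 18").

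The note under the example code in SAP Appendix 4 sets the coding. The censor variable is 1 for a censored time and "has a value = 0 when the event of interest occurs". It adds: "There should be no other values available for this censored variable in this dataset". The appendix describes its code as guidance: "The following SAS code is to be used as a guide for implementation".

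SAP 6.6.1.5 plans a further plot, of time to stopping IP because of an adverse event in the Gastrointestinal Disorders class. It too says that participants who discontinue are censored at that date.

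**The concern.** In a time-to-event display, the outcome being plotted must be the event. Censoring is for people whose follow-up ends without it. SAP 6.5.6 names discontinuation as the outcome and then censors participants at discontinuation. It also does not say when participants who never discontinue leave the risk set.

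The timing of IP stops carries information in this trial. The protocol uses up to 6 weeks for titration, does not allow downward titration, and treats IP discontinuation as one of the two intercurrent events that censor primary endpoint data. These plots are the planned display, by arm, of when IP stops and study exits occur. A programmer who followed the text would remove every event from both. One who noticed would have to depart from the written SAP and invent the missing rule.

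**Working it through.** The documents give no numerical result for these plots, so there is no figure to reproduce. The check sets the rules side by side and then applies them to an illustrative arm.

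**Rules**

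| Item | Source | Content |
|---|---|---|
| Event | SAP 6.5.6 | discontinuation from study; discontinuation of IP (two plots) |
| Censoring of discontinuers | SAP 6.5.6 | censored at the discontinuation date, in both plots |
| Censoring of non-discontinuers | none | not stated |
| Coding | SAP Appendix 4 | 1 = censored, 0 = event, no other value |
| Estimator | SAP 5.2.7 | cumulative incidence without competing risks, i.e. 1 − Kaplan-Meier |

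**Step 1: literal coding.** Discontinuers get 1 under the 6.5.6 sentence. Non-discontinuers have not had the event, so they also get 1. No participant has code 0. The product-limit estimate has no factors, S = 1, and cumulative incidence is 0% throughout, however many discontinue.

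**Step 2: the only other binary coding that obeys the sentence.** Keep discontinuers at 1 and set the others to 0. With 17 of 67 discontinuing, this gives 50 events and a curve that reaches 100%. It plots completion, not discontinuation.

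**Step 3: coding that matches the stated event.** Discontinuers are 0 and the others are 1. If nobody is censored before the last discontinuation, the product telescopes and the final cumulative incidence is k/67 for k discontinuers. Inputs are about 67 per arm and 25% drop-out, from protocol 9.2: 0.25 × 67 = 16.75, rounded to 17, which leaves 50 completers. The values 7 and 25 are an assumed range.

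| k | Discontinuation as event | SAP 6.5.6 as written |
|---|---|---|
| 7 | 7/67 = 10.4% | 0% |
| 17 | 17/67 = 25.4% | 0% |
| 25 | 25/67 = 37.3% | 0% |

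**Step 4: the horizon.** The plots stop at Week 18 (Day 126). Protocol 4.5 places study completion at Visit 11, scheduled for Days 140–147, so a study exit can fall beyond the plot. Each one lowers the correct end value by 1/67 = 1.5 points: with one of 17 exits late, 16/67 = 23.9%; with three, 14/67 = 20.9%. The written rule still gives 0%. This is not part of the error, but it shows that the missing rule for non-discontinuers needs an explicit date.

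**Step 5: SAP 6.6.1.5.** Read literally, its sentence also censors the gastrointestinal stops and gives 0%. Read as covering only stops for other reasons, it is coherent. With g gastrointestinal stops among 17, the end value is then at least g/67 (1.5% at g = 1, 11.9% at g = 8, 25.4% at g = 17), because censoring the other stops can only shrink the risk set. The documents give no gastrointestinal share, so g is purely illustrative.

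**The case against.** The strongest reply is that the intent is plain. SAP 6.5.6 names the event, and Appendix 4 gives code 0 to the event of interest. A programmer working from those two statements would code discontinuation as 0 and draw the right curve. The word censored was probably used loosely, to say that the discontinuation date supplies the time. Literal execution would produce blank plots beside tables full of discontinuations, so the slip would be noticed and could not pass as a plausible result. The plots are exploratory and carry no test, and no estimate or decision rule depends on them.

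The points about intent and limited impact stand. They do not remove the conflict. That Appendix 4 points one way and the 6.5.6 sentence the other is the contradiction itself, and Section 6 is where the SAP sends the reader for the censoring rule. Nor can the sentence be rescued as cross-censoring, with study exit censoring the IP plot or the reverse. It applies to both plots and to the associated date, and the IP plot is defined regardless of study status. SAP 6.6.1.3 shows the correct form in the same document: there, discontinuation censors only when it comes before the adverse event being plotted.

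It is also fair that the percentages above are just k/67 against zero, and that applying the protocol's drop-out assumption to IP stops is a choice made for illustration. On SAP 6.6.1.5 the objection is right that a coherent reading exists. That sentence needs clarifying and is not an error.

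**Conclusion.** The concern holds. The censoring sentence in SAP 6.5.6 contradicts the event it serves. Followed as written under the Appendix 4 coding, it gives 0% in every arm, against 25.4% at 17 of 67 and 10.4% to 37.3% over 7 to 25 of 67. The 0% does not depend on the number of discontinuers. It rests only on non-discontinuers being censored, the one coding open to people without the event. The comparison percentages assume 67 per arm, the 25% drop-out applied to each plot separately (the documents do not split study exits from IP stops), and no censoring before the last discontinuation.

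The consequence is small. SAP 6.5.2 and 6.5.6 tabulate discontinuations, and the weekly denominators in SAP 6.6.1.4 show part of the timing, although they combine IP stops and study exits. No efficacy analysis is touched. This should be corrected, but it does not threaten the trial's conclusions.

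**What to change.** **SAP 6.5.6.** Replace the censoring sentence with a rule for each plot:

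- Study plot: discontinuation from the study is the event (censor = 0) at its date. Participants without it are censored (censor = 1) at the earlier of last observation and Week 18.
- IP plot: discontinuation of IP is the event (censor = 0) at its date. Participants without it are censored (censor = 1) at end of treatment.
- Under protocol 7.2, withdrawal from the study also ends IP. State that a withdrawal during treatment is therefore an event in both plots.

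The essential part is that discontinuation is the event. Other named censoring dates would also work if they respect the Week 18 horizon.

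**SAP 6.6.1.5.** State that stopping IP because of a Gastrointestinal Disorders adverse event is the event, that IP stops for other reasons are censored at their date (in line with the absence of competing risks in SAP 5.2.7), and that completers are censored at end of treatment.

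**Cost.** One sentence replaced and one clarified. No new data, no change to SAP 5.2.7, and no change to the two-value coding in Appendix 4.

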### **6.6. Safety Summaries and Analyses**

The three AEs of interest are: diarrhoea, nausea and vomiting (based on preferred term).

#### **6.6.1. Adverse Events**

Adverse events (Tier 1, 2 and 3 AEs as described in Section 3.5.1) will be summarized by treatment and overall and in accordance with sponsor reporting standards using the safety analysis set defined in Section 4. The adverse events (AEs) will be sorted in descending frequency within a system organ class.

Incidence and severity of treatment emergent adverse event (TEAE) tables will additionally be produced ('All causality' and 'Treatment related', separately) to summarise the total number of adverse events by preferred term, which will be reported by treatment and overall.

The following tables and figures related to TEAEs classed as Tier 1 or 2 will be ordered in descending point estimate of risk difference within System Organ Class. If two or more events have the same frequency they will be sorted alphabetically by preferred term.

TEAEs classed as Tier 1 events will be tabulated by treatment. Number of participants and percent will be presented, along with the risk difference between each dose of PF-06882961 and placebo. 95% confidence intervals and 2-sided p-values will also be presented for the comparison. No adjustment for multiplicity will be used.

Tier 1 TEAEs will also be presented graphically. The TEAEs will be presented in a two-panel plot, the left panel will give the proportions of TEAEs observed in a dose of PF-06882961 and separately placebo while the right panel will display the 95% confidence interval for the risk differences for each TEAE. A vertical line corresponding to the value of 0 will be added to the right-hand plot. For the graphical display for tier 1 events, a column containing the 2-sided p-value for each event will be added to the right-hand side of the forest plot in the right panel. Each panel will be paged by dose of PF-06882961.

TEAEs classed as Tier 2 events will be summarised and graphically presented similar to Tier 1 events, but no p-values will be presented. No adjustments for multiplicity will also be used.

For Tier 1 and Tier 2 outputs, footnotes will be included on the tables to provide proper interpretation of p-values (Tier 1 only) and confidence intervals and to describe how the comparison was conducted, e.g. “P-values and confidence intervals are not adjusted for multiplicity and should be used for screening purpose only. 95% Confidence intervals are provided to help gauge the precision of the estimates for Risk Difference. Risk Difference is computed as PF-06882961 versus placebo.”

It should be recognized that most studies are not designed to reliably demonstrate a causal relationship between the use of a pharmaceutical product and an adverse event or a group of adverse events. Except for select events in unique situations, studies do not employ formal adjudication procedures for the purpose of event classification. As such, safety analysis is generally considered as an exploratory analysis and its purpose is to generate hypotheses for further investigation. The 3-tier approach facilitates this exploratory analysis.

#### **6.6.1.1. Subset reporting interval**

The subset adverse events, described in Section 3.5.1.1, will be summarised as above (excluding the 3-tier reporting system) where standard tables and incidence tables will be produced for both ‘All causality’ and ‘Treatment related’.

#### **6.6.1.2. Hypoglycemic Adverse Events**

The hypoglycemic AEs will be listed in a separate table and summarized categorically by treatment and overall as per Section 5.2.2.

### **6.6.1.3. Time to First Occurrence/Recurrence of AEs of Interest**

Exploratory summaries on the time to the first occurrence of AEs of interest will be produced in Cumulative Incidence Plots as described in Section 5.2.7. Participants who discontinue from the study, discontinue from IP or initiate glycemic rescue medication prior to the start of the AE event of interest will be censored at the discontinuation/initiation date.

The three AEs of interest are: diarrhoea, nausea and vomiting (based on preferred term). A separate plot for each AE will be produced separately.

The above will also be produced separately for the time to the first recurrence of the three AEs of interest.

### **6.6.1.4. Percentage of Participants with Ongoing AEs of Interest**

Exploratory summaries on the percentage of participants reporting AEs of interest will be produced by week and treatment and overall as per Section 5.2.2 from Week 1 up to Week 18 (i.e. including the follow-up visit 10).

To calculate the percentage each week, the total number of participants who experience the TEAE of interest at any time during the respective week will be the numerator and the total number of participants who had not discontinued from IP and/or the study prior to that respective week will be the denominator (note if a participant did discontinue from IP and/or the study during that respective week they would be included in the denominator).

A line plot of the percentages over each week will be produced based on the summary statistics with a separate line for each treatment.

The AEs of interest are diarrhoea, nausea and vomiting (based on preferred term); where a separate table and plot will be produced for each AE.

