## **7. DISCONTINUATION OF STUDY INTERVENTION AND PARTICIPANT DISCONTINUATION/WITHDRAWAL**

### **7.1. Discontinuation of Study Intervention**

It may be necessary for a participant to permanently discontinue IP. If a safety or tolerability concern arises, in particular if not responsive to symptomatic management, dosing with double-blinded IP may be stopped in an individual participant at investigator discretion.

Per the study estimands, if IP is permanently discontinued, the participant will remain in the study and continue to follow all protocol specified visits and procedures according to the SoA with the exception of dosing activities CCI

The site should notify the Sponsor Medical Monitor or Sponsor Clinician if the below criteria for permanent discontinuation are met.

Note that discontinuation of IP does not represent withdrawal from the study.

See the SoA for data to be collected at the time of intervention discontinuation and follow-up and for any further evaluations that need to be completed.

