### **8.3.1. Time Period and Frequency for Collecting AE and SAE Information**

The time period for actively eliciting and collecting AEs and SAEs (“active collection period”) for each participant begins from the time the participant provides informed consent, which is obtained before the participant’s participation in the study (ie, before undergoing any study-related procedure and/or receiving IP), through and including a minimum of 28 calendar days, except as indicated below, after the last administration of the IP.

For participants who are screen failures, the active collection period ends when screen failure status is determined.

Follow-up by the investigator continues throughout and after the active collection period and until the event or its sequelae resolve or stabilize at a level acceptable to the investigator, and Pfizer concurs with that assessment.

Investigators are not obligated to actively seek AEs or SAEs after conclusion of the study participation. However, if the investigator learns of any SAE, including a death, at any time after a participant has been discharged from the study, and he/she considers the event to be reasonably related to the study intervention or study participation, the investigator must promptly notify the sponsor.

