### 3.5. Safety Endpoints

#### 3.5.1. Adverse Events

An adverse event is considered treatment emergent (TEAE) relative to a given treatment if:

- the event starts during the effective duration of treatment (i.e. starting on or after the first dose but before the last dose plus lag time)

The effective duration of treatment is determined by the lag time. Any event occurring within the lag time, whether this occurs during a break in treatment or at the end of treatment, is attributed to the corresponding treatment period. The lag time is defined by the Pfizer Standard of 365 days post last dose of IP.

Adverse events occurring during the placebo run-in period (i.e. starting from Day -14, inclusive, up to and before the first dose of active treatment on Day 1) will be considered non-treatment emergent.

A 3-tier approach will be used to summarize TEAEs. Under this approach, TEAEs are classified into 1 of 3 tiers. Different analyses will be performed for different tiers (see Section 6.6.1).

Tier 1 events: These are prespecified events of clinical importance and are maintained in a list in the product's Safety Review Plan (or similar, e.g. Safety Surveillance Review Plan).

Tier 2 events: These are events that are not tier 1 but are "common." A Medical Dictionary for Regulatory Activities (MedDRA) preferred term (PT) is defined as a Tier 2 event if there are at least 5% of participants reporting the event in any treatment group.

[REDACTED]

Tier 3 events: These are events that are neither Tier 1 nor Tier 2 events.

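### The weekly percentage with nausea, vomiting or diarrhoea removes earlier IP stoppers from the denominator but not from the numerator

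*SAP*

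**What the plan says.** SAP section 6.6.1.4 gives an explicit algorithm for the weekly percentage. For the top line, "the total number of participants who experience the TEAE of interest at any time during the respective week will be the numerator". For the bottom line, "the total number of participants who had not discontinued from IP and/or the study prior to that respective week will be the denominator". The one clarifying note concerns the denominator: "if a participant did discontinue from IP and/or the study during that respective week they would be included in the denominator". Nothing limits the numerator to people in the denominator. The display covers Weeks 1 to 18, by treatment and overall, with a separate table and line plot for each of the three events.

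Four other provisions decide who can reach the numerator:

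- Protocol 7.1: after permanent discontinuation of IP, "the participant will remain in the study and continue to follow all protocol specified visits and procedures", apart from dosing activities.
- Protocol 8.3.1: adverse events are actively collected "through and including a minimum of 28 calendar days, except as indicated below, after the last administration of the IP".
- SAP 3.5.1, on the treatment-emergent window: "The lag time is defined by the Pfizer Standard of 365 days post last dose of IP".
- SAP 3.5.1.1 defines a shorter window, to two days after the last dose, but for a separate subset summary. Section 6.6.1.4 does not refer to it.

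The neighbouring section 6.6.1.3 (time to first occurrence or recurrence) does state a rule: participants who "discontinue from IP or initiate glycemic rescue medication prior to the start of the AE event of interest will be censored" at that date.

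**The concern.** A percentage of participants should have a numerator drawn from its denominator. Here a participant whose nausea starts on IP, who stops IP in Week 5 and is still nauseated in Week 6, is in both parts in Week 5 and in the numerator alone in Week 6. The section is about ongoing events, so no new onset is needed.

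The case is foreseeable. Protocol 4.2 does not permit downward titration and says that participants who cannot tolerate the scheme or dose may have to stop IP. SAP 6.6.1.5 plans a plot of IP discontinuation due to gastrointestinal events. The people leaving the denominator therefore include those with the events being counted.

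What is at stake is the week-by-week comparison of gastrointestinal tolerability between arms. Tolerability across dose levels is a secondary objective, and the study is meant to support dose selection (Protocol sections 2.1 and 3). An artefact that varies by arm and week could be read as a dose or titration effect.

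**Working it through.** The documents give no figure for this percentage and no by-arm discontinuation or event rates, so there is no planned value to reproduce. From Protocol 9.2 I take about 67 participants per arm and a 25% drop-out assumption (67 × 0.75 = 50.25, about 50 completers). Drop-out from the study is only a proxy for having stopped IP. All event rates below are assumptions.

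**Counts.** For one arm and week, let D be the participants not previously discontinued, x the cases among them, y the cases among earlier stoppers, and N all participants followed.

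- As written: (x + y)/D
- Numerator limited to the denominator: x/D
- All followed, in both parts: (x + y)/N

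The excess of the literal figure over x/D is y/D. It is never negative, and it is zero when y = 0. One case among earlier stoppers adds 1/60 = 1.7 points at D = 60, 1/50 = 2.0 at D = 50 and 1/40 = 2.5 at D = 40.

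Example with N = 67, 17 earlier stoppers all still followed, D = 50, x = 5, y = 2:

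- As written: 7/50 = 14.0%
- Limited to the denominator: 5/50 = 10.0%
- All followed: 7/67 = 10.4%

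The ratio is not bounded by 100%: D = 30, x = 15, y = 16 gives 31/30 = 103%. That is unlikely, but it shows that the quantity is not a proportion.

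**Rates.** Let d be the fraction already discontinued, r_on the weekly event rate among those not discontinued, and r_off the rate among those who are.

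Literal = [(1 − d)·r_on + d·r_off]/(1 − d) = r_on + r_off·d/(1 − d)

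With r_on = 20%:

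| d | d/(1 − d) | r_off = 0% | 5% | 10% | 20% |
|---|---|---|---|---|---|
| 5% | 0.053 | 20.0% | 20.3% | 20.5% | 21.1% |
| 10% | 0.111 | 20.0% | 20.6% | 21.1% | 22.2% |
| 25% | 0.333 | 20.0% | 21.7% | 23.3% | 26.7% |

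**Against the percentage of all participants.** The numerators are the same, so the literal figure is larger by the factor 1/(1 − d): 1.05, 1.11, 1.33 and 1.67 at d = 5%, 10%, 25% and 40%. For a comparison with only those still in the study, d must be counted among them, so the factor is smaller if anyone has left.

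**Does the arm with most discontinuation suffer most?** Not necessarily. In an arm of 67, 17 stoppers with no event add 0/50 = 0 points, while 3 stoppers with one event add 1/64 = 1.6 points. Both the discontinuation rate and the event rate among stoppers matter.

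**Weeks 17-18.** Treatment lasts 16 weeks, so in these weeks everyone should be off IP. If completing treatment is not discontinuing, completers stay in the denominator while early stoppers, equally off drug, can appear only in the numerator.

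**The case against.** The best defence is that a section headed as a percentage of participants, referring to the ordinary categorical summary in SAP 5.2.2, would naturally be programmed by counting cases among those in the denominator. Keeping participants in the denominator for the week they stop also suggests an on-IP display. That may well be the intent. But the text spells out each part of the ratio separately, and the SAP's version history says this calculation was added to make the algorithm clear. A programmer who adds the filter is supplying a rule the SAP does not contain.

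Several narrower points have weight:

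- The 25% is a study drop-out rate. Participants who have left the study mostly stop contributing events, so a full off-IP event rate applied to all of them is high. The 26.7% belongs at the upper end of the range, and the columns at 0% and 5% cover the milder case.
- The value d = 40% has no source in the documents and only shows how the factor behaves.
- SAP 3.5.1.1 and 6.1.1.1 treat completing 16 weeks as distinct from discontinuing, which favours keeping completers in the denominator. Section 6.6.1.4 does not say so, and that reading is the one that produces the Week 17-18 asymmetry.
- Section 6.6.1.3 also censors at glycaemic rescue, so matching the numerator here would align the two displays on IP discontinuation only.
- The display is labelled exploratory, and no hypothesis or stopping criterion in the documents refers to it.

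These points limit the size and reach of the problem. They do not make the written ratio coherent.

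**Conclusion.** The concern holds. Followed literally, the rule can give a figure that describes neither participants still on IP nor all participants followed. It can only overstate the percentage among those not discontinued, by y/D: nothing when no earlier stopper has the event, and 6.7 points in the most extreme tabulated case (d = 25%, with 20% event rates both on and off IP). The actual size cannot be known from the documents.

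The reach is narrow: one exploratory table and line plot for each of three events. Primary and secondary efficacy inference, the overall treatment-emergent tables, the two-day subset summary and the time-to-event plots are unaffected. It should still be corrected, because the display compares tolerability between doses over time and the distortion can differ by arm and week.

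**What to change.** Use one set for both parts. The simplest change is to define the numerator as participants in that week's denominator who experience the event at any time during the week. This fits the handling of IP discontinuation in section 6.6.1.3. The price is that ongoing events in people who have stopped IP drop out of this display; they remain in the overall treatment-emergent tables.

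If events after stopping IP are wanted here, use all participants still in the study for both numerator and denominator, which is equally coherent. Either way, name the set in the text and in the table and figure footnotes, and say whether participants who completed 16 weeks count as not discontinued in Weeks 17 and 18.

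The cost is a short SAP edit (one clause for the numerator, plus the completer rule) and one filter in the program. No other analysis changes.
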